 - SMMSE: 30-point validated test used to examine the cognitive mental status of a subject. The SMMSE measures various domains of cognitive functions including orientation to time and place; registration; concentration; short-term memory; naming familiar items; repeating a common expression; and the ability to read and follow written instructions. The resulting total score is corrected for degree of schooling and age.
- Proportion of subjects with evidence of cardiac ischemia and/or arrhythmia/conduction abnormalities on Days 1, 2, 3, and 4, and Weeks 1 and 5 of 30-day post-daily PE treatment period, and the first and final FU visit.
- Proportion of subjects who have a platelet count $\geq 150 \times 10^9/L$ on Day 1, 2, 3, 4, 5 and Day 10 and at end of study drug treatment (i.e., last weekly visit during the treatment period).
- Proportion of subjects with refractory TTP, defined according to Scully et al. (2016) as lack of sustained platelet count increment or platelet counts $< 50 \times 10^9/L$ and persistently raised LDH ($> 1.5 \times \text{ULN}$) despite 5 plasma exchanges and steroid treatment.
- Time to stop of daily PE.
- Bleeding events.
- (S)AEs, laboratory data, vital signs, ECG and physical examinations.
- PE parameters: number of days and total volume in 2 time periods, i.e. DB treatment daily PE period and overall treatment period.
- Number of days in ICU and in hospital in 4 time periods: DB treatment daily PE period, overall treatment period, FU period (of 4 weeks after stop of study treatment) and overall study period.
- PD parameters: vWF: Ag concentration, FVIII: C activity and RICO activity.
- PK parameters: study drug concentrations.
- Immunogenicity: ADA, mADA, NAb, and alternative NAb.

Note: The components of composite key secondary endpoints (both proportion of subjects and number of events) will also be analyzed separately as 'other secondary endpoint'.

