6.2 Secondary Efficacy Endpoints Evaluation

6.2.1 Key secondary endpoints

Key secondary endpoints are defined in Section [3.3.2.1](#).

Confirmatory hypothesis testing will be conducted only for the key secondary endpoints. In order to control the rate of false positive conclusions with a family-wise error rate of 5%, a fixed sequence approach will be applied. The key secondary endpoints are hierarchically ordered. This allows statistical testing for these endpoints at the same nominal significance level of 5% without adjustment, as long as the tests occur in the pre-defined sequential order, and given that all null hypotheses to be tested for endpoints with a higher rank (including the primary endpoint) are rejected. As soon as a test is not statistically significant for a certain endpoint, i.e. as soon as the sequence breaks, no confirmatory testing will be done for remaining endpoints lower in the ranking. Statistical comparison between the two treatment arms for the key secondary endpoints will be done by means of the following planned analyses (in hierarchical order):

1. Proportion of subjects with TTP-related death, a recurrence of TTP, or at least one treatment-emergent major thromboembolic event (e.g., myocardial infarction, cerebrovascular accident, pulmonary embolism or deep venous thrombosis [DVT]) during the overall treatment period (including extensions). Start and end times of the overall treatment period are defined in Section [4.4.1](#). A Cochran-Mantel-Haenszel (CMH) test will be conducted with adjustment for GCS category (stratification factor used in randomization). For both treatment groups, only events that have occurred prior to a switch to open-label caplacizumab will be evaluated for this analysis.

This composite endpoint consists of the following components:

- TTP-related death: adverse event categorized as 'clinically significant TTP event' and documented as 'death due to TTP' and/or adverse events with outcome 'fatal', adjudicated as TTP related (see below).
- TTP recurrence: recurrent thrombocytopenia after initial recovery of platelet count, requiring re-initiation of daily PE. Depending on the timing of recurrence, it is defined as:
 - Exacerbation: recurrence occurring during the first 30-days post-daily PE period
 - Relapse: recurrence occurring after the 30-days post-daily PE period; only relapses within the overall treatment period are taken into account for the key secondary endpoint.

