Exacerbations and relapses will be documented as serious adverse events. Note that, exceptionally, daily PE may have been stopped before an initial platelet count $\geq 150 \times 10^9/L$ is reached, by investigator's decision. It is recognized that in this case the subject can still experience an exacerbation or relapse requiring re-initiation of daily PE if documented as described above.

- Treatment-emergent major thromboembolic event: e.g., myocardial infarction, cerebrovascular accident, pulmonary embolism or DVT, confirmed after adjudication (see below).

If a potential major thromboembolic event or TTP-related death occurs, the investigator will be requested to provide additional information for adjudication by a blinded independent committee. Only events that are confirmed after adjudication will be used for the analysis. More details are provided in CSP Section 3.4.3.6 and [Appendix B: Adjudication charter](#).

2. Proportion of subjects with a recurrence of TTP in the overall study period (including the FU period). A CMH test will be conducted with adjustment for GCS category (stratification factor used in randomization). For both treatment groups, only recurrences that have occurred prior to a potential switch to open-label caplacizumab will be evaluated for this analysis.
3. Proportion of subjects with refractory TTP, defined as absence of platelet count doubling after 4 days of standard treatment, and LDH $>$ ULN. A CMH test will be conducted with adjustment for GCS category (stratification factor used in randomization). Refractory TTP is derived as follows: (platelet count after 4 days of standard treatment / platelet count at start of standard treatment) $<$ 2 and LDH $>$ ULN after 4 days of standard treatment. Platelet count and LDH at Day 5 will be used for this analysis. Subjects who have reached platelet count response (primary endpoint) by Day 5 will not be considered as having a refractory TTP.

Subjects discontinued (lost to follow-up, withdrew consent, etc...) before day 5 will be excluded from the analysis.

CONFIDENTIAL

Missing values will be imputed using multiple imputation (Markov Chain Monte Carlo) by averaged simulated parameter values. The number of simulation iterations will be adapted to the proportion of missing values (0-10% missing values: 20 iterations, 10-20% missing values: 100 iterations) to keep the relative efficiency (RE) of multiple imputation under control (Rubin, 1987).

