- Proportion of subjects who have a platelet count $\geq 150 \times 10^9/L$ on Day 1, 2, 3, 4, 5 and Day 10 and end of study drug treatment (i.e., last weekly visit during the DB or OL treatment period) will be summarized by treatment group (Caplacizumab, Placebo, OL Caplacizumab).
- Proportion of subjects with refractory TTP, defined according to Scully et al. (2016) as lack of sustained platelet count increment or platelet counts $< 50 \times 10^9/L$ and persistently raised LDH ($> 1.5 \times$ ULN) despite 5 plasma exchanges and steroid treatment will be summarized by treatment group (Caplacizumab, Placebo). Refractory TTP is derived as follows: (platelet count at Day x $<$ platelet count at Day x-1 for at least 1 value of x with x=2,...,5) and (LDH $> 1.5 \times$ ULN from Day 1 to Day 5). Subjects who have reached platelet count response (primary endpoint) by Day 5 will be considered as not refractory to TTP. Missing values will be imputed by using multiple imputation (Markov Chain Monte Carlo) by

averaged simulated parameter values, except if the subject discontinued prior to Day 5. In that case, the subject will not be considered in the analysis.

- Time to stop of daily PE: A KM analysis will be conducted with time to stop of daily PE within the DB treatment period as dependent variable and treatment group (Caplacizumab, Placebo) as independent variable. Time to stop of daily PE is defined as: date of daily PE stop - date of first i.v. loading dose of study drug after randomization + 1 day.
- The number of PE days and the total PE volume (absolute and normalized) in the DB treatment daily PE period and the overall treatment period will be summarized by treatment group. For this analysis the treatment groups are defined as
 - Caplacizumab + OL Caplacizumab
 - Placebo + OL Caplacizumab

Subjects will thus be analyzed according to their initial treatment group, both before and after switch to open-label caplacizumab. The number of PE days is defined as the total number of days on which PE is documented. The absolute total PE volume is given by the sum over all PE days of the amount exchanged in liter, while the normalized total PE volume is calculated as the sum over all PE days of the multiple of plasma volume exchanged.

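### Among subjects with persistently raised LDH and no platelet response by Day 5, the consensus-based refractory TTP derivation flags any one-day dip and drops the stated <50 x 10^9/L alternative

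*SAP*

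**What the plan says.** SAP 3.3.2.2 and 6.2.2 list a version of refractory TTP taken from a published consensus. Its platelet criterion is "lack of sustained platelet count increment or platelet counts" below 50 x 10^9/L. It is combined with LDH persistently above 1.5 x ULN, "despite 5 plasma exchanges and steroid treatment".

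The same bullet of 6.2.2 then gives the derivation, which has three parts:

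- Platelets: the count at Day x is below the "platelet count at Day x-1 for at least 1 value of x with x=2,...,5".
- LDH, joined by *and*: above 1.5 x "ULN from Day 1 to Day 5".
- Exemption: "Subjects who have reached platelet count response (primary endpoint) by Day 5 will be considered as not refractory to TTP".

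The result goes to Table 14.2.1.2.4. It is separate from the third key secondary endpoint (SAP 6.2.1, Table 14.2.1.2.3), which defines refractory TTP as "absence of platelet count doubling after 4 days of standard treatment" with LDH above ULN and compares Day 5 with the start of treatment. On inference, SAP 6.2.1 states: "Confirmatory hypothesis testing will be conducted only for the key secondary endpoints".

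**The concern.** The derivation should turn the stated definition into code, and it departs from it in two places.

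First, a sustained increment describes the course of the count over the treatment window. The rule tests each of four daily steps and is met by one fall of any size, whatever follows. It has no minimum fall, no confirmation, and no comparison of Day 5 with Day 1.

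Second, the definition offers an alternative platelet criterion, a count below 50 x 10^9/L. The derivation does not contain it.

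The table will be read as following the consensus definition. If the code measures something else, the proportion refractory is hard to interpret. It may also disagree with the key secondary table for individual patients because of coding rather than biology.

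**Working it through.** The documents give no figure for this endpoint, so there is nothing to reproduce. The check applies the written rules to example series and then asks how often a truly rising count dips.

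**Rules, for a subject with LDH above 1.5 x ULN on Days 1 to 5 and no primary response by Day 5** (P1 to P5 are the Day 1 to Day 5 counts, x 10^9/L):

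- SAP 6.2.2 derivation: refractory if P2<P1, or P3<P2, or P4<P3, or P5<P4.
- SAP 6.2.1 key secondary: refractory if P5/P1 < 2 (its LDH condition, above ULN, is already met).

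| P1 to P5 | P5/P1 | SAP 6.2.2 derivation | SAP 6.2.1 rule |
|---|---|---|---|
| 12, 40, 85, 82, 130 | 130/12 = 10.8 | refractory (82<85) | not refractory |
| 20, 45, 40, 90, 140 | 140/20 = 7.0 | refractory (40<45) | not refractory |
| 10, 11, 12, 13, 14 | 14/10 = 1.4 | not refractory (no fall) | refractory |
| 10, 10, 10, 10, 10 | 1.0 | not refractory (no fall) | refractory |
| 30, 25, 20, 15, 12 | 12/30 = 0.4 | refractory | refractory |

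Rows 1 and 2 are over-inclusion. Rows 3 and 4 are under-inclusion: all counts are below 50, so the stated alternative is met. If LDH in row 2 falls to 1.5 x ULN or below by Day 4, that subject is not flagged. A subject with a dip and primary response by Day 5 is not flagged either.

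**How often a rising count dips.** The documents give no day-to-day CV, growth rate or spread, so these are assumptions: start at 25, constant growth factor g per day, independent log-normal daily variation, counts rounded to whole numbers. For one step, before rounding, P(dip) = Φ(−ln g / (σ√2)), with σ² = ln(1+CV²). For g = 1.3 and CV 10%: σ = 0.0998, 0.2624/0.1411 = 1.86, Φ(−1.86) = 0.031. Four steps give at most 4 x 0.031 = 0.126. Simulation over four steps gives:

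| Growth per day (rise by Day 5) | CV 10% | CV 15% | CV 20% |
|---|---|---|---|
| 1.3 (1.3^4 = 2.9-fold) | 10% | 36% | 56% |
| 1.4 (1.4^4 = 3.8-fold) | 3% | 19% | 39% |

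For a mixed population, growth was set at about 1.45 per day with a log SD of 0.2, and non-response meant no count of 150 or more by Day 5. Among non-responders meeting the platelet rule, roughly 20%, 41% and 51% at the three CVs had a Day 5 count of at least 50 and at least double Day 1. In the other direction, the rule missed about 7% to 28% of non-responders with a Day 5 count below 50, with most missed at the lowest CV.

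All simulated figures concern the platelet part only, before the LDH condition.

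**The case against.** The strongest reply has three parts.

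**A dip alone is not enough.** LDH must stay above 1.5 x ULN from Day 1 to Day 5, and early responders are exempt. This stands: the problem concerns only subjects who pass both conditions. Those conditions narrow the group but do not repair the platelet rule within it.

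**The endpoint is descriptive.** This also stands. The confirmatory refractory endpoint already compares Day 5 with the start of treatment and is untouched.

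**The SAP sets no threshold for a sustained increment, so any coding is a choice.** This is partly right. Net change is one reasonable reading, not the only one. But a dip that is recovered, within a tenfold rise, does not show that a sustained increment is lacking. The missing 50 x 10^9/L alternative is an omission, not a matter of interpretation.

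A reader might go further and infer that the rule inflates the proportion in both arms and dilutes the contrast. Another might infer that it loads the excess onto placebo, because the SAP assumes a median time to response of 7 days there against 4.2 days on caplacizumab. The documents support neither inference. The two errors run in opposite directions, and no document gives day-to-day variability, growth rates or LDH courses by arm.

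**Conclusion.** The concern holds in a limited form. The SAP 6.2.2 derivation does not implement the definition in its own paragraph and in 3.3.2.2, and it misclassifies in both directions. That follows from the wording alone and needs no assumption.

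The size is not established. The simulated rates rest on assumed CVs and growth, depend on how the patient mix is specified, and precede the LDH condition. They show that a dip in a rising count can be rare (3% at 1.4-fold daily growth and 10% CV) or common (56% at 1.3-fold and 20% CV). They do not estimate the error in Table 14.2.1.2.4. The change is worth making because the table is presented as a published standard, but it is not critical to the trial's conclusions.

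**What to change.** Before database lock, replace the platelet part of the derivation in SAP 6.2.2, and use the same rule for Table 14.2.1.2.4:

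*(platelet count at Day 5 ≤ platelet count at Day 1, or platelet count at Day 5 < 50 x 10^9/L)*

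Keep the LDH condition (above 1.5 x ULN from Day 1 to Day 5) and the exemption for primary response by Day 5.

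Under this rule 12, 40, 85, 82, 130 and 20, 45, 40, 90, 140 become not refractory. The series 10, 11, 12, 13, 14 and the constant 10 become refractory, and 30, 25, 20, 15, 12 stays refractory. By construction it cannot flag a subject whose Day 5 count is at least 50 and at least double Day 1.

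Both halves are needed. Day 5 not above Day 1 on its own would miss 20, 90, 70, 40, 25, a lost increment ending below 50. In the mixed population above it would miss about 75% to 78% of non-responders with a Day 5 count below 50.

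One limit remains: an increment partly lost but still above both 50 and Day 1 at Day 5 is not flagged. Keeping the current derivation as a supportive tabulation would show such cases.

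The cost is one line of SAP wording and one of programming. Daily platelet counts and LDH are already scheduled over these days.

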Results from the caplacizumab arm suggest that ADAMTS13 activity data could identify subjects who were at risk for early relapse. In 7 of 8 subjects with a relapse in the first month, it occurred within 4-10 days after stopping caplacizumab. All 7 subjects had ADAMTS13 activity values <10% at baseline, during and near the end of the treatment period, indicating unresolved underlying disease activity. In the 8th subject, the relapse event occurred at 30 days after stopping caplacizumab treatment. This subject had normalization of ADAMTS13 activity during and near the end of the treatment period. However at the time of the relapse, ADAMTS13 activity was again suppressed <10%, which suggests a *de novo* TTP event. Conversely, 22 caplacizumab-treated subjects did not have an exacerbation or relapse, with ADAMTS13 activity data available near the end of the treatment period for 16/22 patients. In 13 of 16 subjects without exacerbation or relapse, ADAMTS13 activity had returned to values \geq 10% near the end of the treatment. ADAMTS13 activity results from the placebo treated subjects supported the potential predictive value of the marker: for 14 of 16 placebo subjects without exacerbation or relapse (ADAMTS13 data available for 16/23 placebo subjects), ADAMTS13 activity values were \geq 10% near the end of the placebo treatment period. A total of 11 placebo subjects had an exacerbation during the treatment period, and ADAMTS13 activity data were available for 8 of them. Seven of 8 placebo subjects with an exacerbation had ADAMTS13 activity <10% around the time of the exacerbation, while the 8th subject had a borderline ADAMTS13 activity value of 11%. In summary, the data support ADAMTS13 activity as a potential marker to identify patients at risk for exacerbation or relapse, specifically patients with signs of ongoing active disease during the treatment period who are at risk of relapse early after stopping caplacizumab treatment.

No significant unanticipated safety concerns were raised for treatment with caplacizumab in this study. The results were as expected for the population of patients with acquired TTP. The overall duration of exposure to study drug was similar in the two treatment arms.

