In case a subject has a TTP recurrence while still receiving study drug in the treatment extension period and has not had a prior exacerbation, then daily PE should be started as part of standard of care treatment together with appropriate immunosuppressive treatment. Study drug treatment will crossover as open-label caplacizumab irrespective of what the initial treatment allocation was without breaking the blind of the initial treatment assignment. Caplacizumab treatment and visit schedule will be the same as during the initial treatment period, covering i.v. bolus, daily PE (variable duration), 30-days post-daily PE and possible treatment extension. This will apply only for the first relapse. In case of further exacerbation or relapse in the subsequent treatment period, study drug will be discontinued. In case a subject has subsequent relapses, standard of care treatment of daily PE and appropriate immunosuppressive treatment should be initiated as per site practice. There will be no re-initiation of study drug administration for a second or further relapse.

Relapse during the 4-week FU period

In case a subject has a first or subsequent TTP relapse in the FU period after completing study drug treatment, standard of care treatment of daily PE and appropriate immunosuppressive treatment should be initiated as per site practice. There will be no re-initiation of study drug administration.

As stated above, there will be no re-initiation of study drug administration for subjects experiencing more than one exacerbation or relapse (or an exacerbation after a relapse or a relapse after an exacerbation).

Subjects on treatment experiencing a second exacerbation or a second relapse, or a relapse after an exacerbation, or an exacerbation after a relapse should return for a "second or subsequent recurrence visit" at the time of initiating the daily PE and the final FU visit to undergo the assessments as specified in the [Schedules of Assessments](#).

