- Proportion of subjects with neurological symptoms based on neurological assessment on Day 1, 2, 3, 4, 5 and Weeks 1 and 5 of 30-day post-daily PE treatment period, and the first and final FU visit.
- Change from baseline in SMMSE total score on Days 1, 2, 3, 4, 5 and Weeks 1 and 5 of the 30-day post-daily PE treatment period, and the first and final FU visit.
- Proportion of subjects with evidence of cardiac ischemia and/or arrhythmia/conduction abnormalities on Days 1, 2, 3, and 4, and Weeks 1 and 5 of 30-day post-daily PE treatment period, and the first and final FU visit.
- Proportion of subjects who have a platelet count $\geq 150 \times 10^9/L$ on Day 1, 2, 3, 4, 5 and Day 10 and end of study drug treatment (i.e., last weekly visit during the study drug treatment period).

- Time to stop of daily PE.
- Bleeding events.
- Proportion of subjects with at least one treatment-emergent thromboembolic event (based on the Standardized MedDRA Query [SMQ] Embolic and thrombotic events [arterial, venous, and vessel type unspecified and mixed arterial and venous]).
- (S)AEs.
- PE parameters: number of days and total volume (absolute and normalized) in 2 time periods: initial daily PE period and full study drug treatment period.
- Number of days in ICU and in hospital in 4 time periods: initial daily PE period, full study drug treatment period, in the FU period (of 4 weeks after stop of study treatment) and overall study period.
- PD parameters: vWF, FVIII, RICO.
- PK parameters.
- Immunogenicity (ADA).

Note: The components of composite key secondary endpoints will also be analyzed separately as 'other secondary endpoint'.

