4.4 Analysis Periods and Visit Windows

4.4.1 Analysis periods

The following analysis phases are defined for this study: Screening, Treatment, Follow-up. Within these analysis phases, the following analysis periods and subperiods will be considered:

Table 1: Analysis periods

Period	Subperiod	Start period	End period
(Screening)		Date of signing the ICF, with 00:00 added as timepart	First DB treatment administration datetime – 1 min
Double-Blind (DB) Treatment	Daily PE	First administration datetime of DB treatment	Start of DB post-daily PE subperiod – 1 min
	Post-daily PE	Date of switch to post-daily PE + 1 day with 00:00 added as timepart	Min(Week 5 visit date if no treatment extension or last visit date of treatment extension period with 23:59 added as timepart, early termination visit date with 23:59 added as timepart, first administration datetime of OL treatment – 1 min)
	Daily PE	First administration datetime of OL treatment	Start of OL post-daily PE subperiod – 1 min

CONFIDENTIAL

Open-label (OL) Treatment	Post-daily PE	Date of switch to post-daily PE + 1 day with 00:00 added as timepart	Min(Week 5 visit date if no treatment extension or last visit date of treatment extension period, early termination visit date) with 23:59 added as timepart
(Follow-up)		End of treatment period + 1 min	Trial termination date, with 23:59 added as timepart

Note that the last analysis period in case of early termination will always be ended by the trial termination date.

The 'overall treatment period' corresponds with the treatment analysis phase and covers both the DB treatment analysis period and the OL treatment analysis period. Note that only subjects who experience a relapse or exacerbation will have an OL treatment analysis period. For these subjects, the overall treatment period starts at start of DB treatment period and ends at end of OL treatment period. For subjects with no switch to open-label caplacizumab, the overall treatment period starts at start of DB treatment period and ends at end of DB treatment period.

The 'overall study period' covers both the treatment analysis phase and the follow-up analysis phase.

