- Number of days in ICU and in hospital will be summarized by treatment group (Caplacizumab + OL Caplacizumab, Placebo + OL Caplacizumab) in the DB treatment daily PE period, in the overall treatment period, in the FU period and in the overall study period. The number of days in ICU is calculated as (ICU discharge date – ICU admission date + 1 day) summed over all stays in ICU. The number of days in hospital is calculated as (discharge date – admission date + 1 day) summed over all hospitalizations (including days in ICU). Subjects will be analyzed according to their initial treatment group, both before and after switch to open-label caplacizumab.

A detailed list of tables, listings and figures can be found in Section [14.2](#), Section [16.2](#) and Section [15.1](#), respectively.

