14.2.5 Plasma exchange

Table 14.2.1.5.1: EFF: Plasma Exchange – Time to stop of daily PE

Kaplan-Meier analysis. The output will include number of events, number of censored values, median, 25% and 75% time to event with 95% CIs.

Population: ITT population.

Table 14.2.1.5.2: EFF: Plasma Exchange – Number of days of PE

Descriptive statistics of the number of days of PE, in the DB treatment daily PE period and in the overall treatment period separately.

Population: ITT population.

Table 14.2.1.5.3: EFF: Plasma Exchange – Total volume of PE (absolute)

Descriptive statistics of the total volume of PE (absolute), in the DB treatment daily PE period and in the overall treatment period separately.

Population: ITT population.

Table 14.2.1.5.4: EFF: Plasma Exchange – Total volume of PE (normalized)

Descriptive statistics of the total volume of PE (normalized), in the DB treatment daily PE period and in the overall treatment period separately.

Population: ITT population.

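### Plasma-exchange days and volume are not summarized for follow-up, so exchange given for relapses after the treatment period enters no visible summary table

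*SAP*

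**What the plan says.** Protocol 3.6.4 defines the PE parameters as "number of days and total volume (absolute and normalized) in 2 time periods: initial daily PE period and full study drug treatment period". SAP 3.3.2.2 and 6.2.2 keep those two windows: by SAP 6.2.2, PE days and volume "in the DB treatment daily PE period and the overall treatment period will be summarized by treatment group". Among the outputs, Table 14.2.1.5.2 is specified as "Descriptive statistics of the number of days of PE, in the DB treatment daily PE period and in the overall treatment period separately". The two volume tables, 14.2.1.5.3 and 14.2.1.5.4, follow the same pattern. Subjects stay in their initial arm before and after any switch to open-label drug.

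SAP 4.4.1 fixes the boundaries. The overall treatment period "covers both the DB treatment analysis period and the OL treatment analysis period". Without a switch it closes at the Week 5, last extension or early termination visit, and follow-up begins one minute later.

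The handling of recurrences decides which window their PE falls into:

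- **On treatment.** A first exacerbation, or a first relapse during treatment extension, leads to daily PE together with open-label caplacizumab (protocol 3.1.1). That PE lies in the open-label period and is counted.
- **In follow-up.** The wording of protocol 3.3 runs: "first or subsequent TTP relapse in the FU period after completing study drug treatment, standard of care treatment of daily PE". Immunosuppression is added, but study drug is not restarted. No open-label period opens, so that PE lies in follow-up.

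Hospital and ICU days are handled differently. They are summarized "in the DB treatment daily PE period, in the overall treatment period, in the FU period and in the overall study period", by initial arm.

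**The concern.** The effect on PE days and volume is a stated secondary objective (protocol section 2), and that objective is not limited to the time on study drug. ICU and hospital days stand in the same bullet and are followed to the end of the study. PE is not, and neither document gives a reason.

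The protocol itself makes the timing of recurrence an issue. It does not expect the drug to act on the autoimmune trigger (3.1.2). It also suggests that shorter PE in the Phase II caplacizumab arm may have affected when the underlying disorder resolved (1.2.4). On Phase II timing it reports: "In 7 of 8 subjects with a relapse in the first month, it occurred within 4-10 days after stopping caplacizumab". If recurrences in one arm tend to come after treatment ends, a window that closes at the end of treatment shows the initial reduction in PE but not the later use. The planned tables could then not distinguish PE that was avoided from PE that was postponed.

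**Working it through.** **Inputs from protocol 1.2.4 (Phase II)**

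- Mean PE days in the initial daily PE period: 5.9 caplacizumab, 7.9 placebo.
- Subjects with an exacerbation during treatment: 3 versus 11.
- Subjects with an exacerbation and/or relapse, including one month of follow-up: 10 versus 11.
- Arm sizes: complete remission in 29 subjects (80.6%) and 18 subjects (46.2%), with 75 enrolled, gives 36 and 39.

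**Reproducing the stated percentages.** 3/36 = 8.3%, 11/39 = 28.2%, 10/36 = 27.8%. All agree with the protocol (8%, 28%, 27.8%, 28.2%).

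**Assumption.** The documents do not say how many PE days a recurrence takes. Call it d, equal in both arms. Using the two initial-episode means as a guide gives 5.9 to 7.9 days; 4 to 10 days is a wider check.

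**Formula.** Mean PE days in a window = initial-period mean + (subjects with a recurrence in the window / n) × d.

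| d | Placebo, either window | Caplacizumab, planned window | Difference, planned | Caplacizumab, whole study | Difference, whole study | Excess = 7/36 × d |
|---|---|---|---|---|---|---|
| 4 | 9.03 | 6.23 | 2.79 | 7.01 | 2.02 | 0.78 |
| 5.9 | 9.56 | 6.39 | 3.17 | 7.54 | 2.03 | 1.15 |
| 7.9 | 10.13 | 6.56 | 3.57 | 8.09 | 2.03 | 1.54 |
| 10 | 10.72 | 6.73 | 3.99 | 8.68 | 2.04 | 1.94 |

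Placebo = 7.9 + 11/39 × d. Caplacizumab = 5.9 + 3/36 × d in the planned window and 5.9 + 10/36 × d over the whole study. In relative terms, for d of 5.9 to 7.9, a reduction of 33% to 35% in the planned window becomes 20% to 21% over the whole study.

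**Why 7 and not 8.** The protocol mentions 8 caplacizumab subjects with a relapse. But 3 + 8 = 11 exceeds the 10 subjects with any recurrence, so one subject apparently had both. The placebo figure is a count of subjects, so the like-for-like caplacizumab figure is 10 − 3 = 7 subjects.

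**Effect of treatment extension.** If extension halved the follow-up relapses, the excess would be 0.5 × 7/36 × d, which is 0.57 days at d = 5.9 and 0.77 days at d = 7.9.

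**Volume.** The same recurrence shares apply, but the documents give no volume per recurrence, so no figure is put on it here.

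**The case against.** Several points can be made for the plan as it stands.

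- **The rule is neutral between arms.** PE for a caplacizumab exacerbation is counted, and PE for a placebo relapse in follow-up is not. This stands: any imbalance comes from when recurrences happen, not from the rule.
- **The data are not lost.** PE is listed by subject (Listings 16.2.2.7 and 16.2.3.5), and the exploratory sections (SAP 6.4 and 14.2.8) are not readable in the public version, so a further PE summary cannot be excluded. A listing is still not a comparison of arms, and the tables for the stated endpoint do not cover follow-up.
- **Late relapse is visible elsewhere.** Recurrence over the whole study is the second key secondary endpoint, and recurrences during and after study drug are summarized separately. A reader would see the late events. The PE they consumed would still be missing.
- **The Phase II projection is uncertain.** That placebo had no relapse in follow-up is inferred from subject counts only. Each such relapse would take 1/39 × d, or 0.15 to 0.20 days, off the excess. All 7 subjects who relapsed within 4 to 10 days had ADAMTS13 activity below 10% near the end of treatment, and this trial extends treatment for that profile. Halving is one scenario; a larger fall is also possible.
- **The boundary is a visit, not the last dose.** After early discontinuation, PE before the early termination visit is counted. SAP 4.4.1 also says that with early termination the last analysis period runs to trial termination, so some PE after drug stop may be included.

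These points limit the size and the certainty of the concern. They do not close the gap in the summaries.

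**Conclusion.** The gap is real: no visible summary table covers PE given for a relapse in follow-up, whereas PE for an on-treatment exacerbation is included. On Phase II timing the planned window would show a difference larger by 1.1 to 1.5 PE days per subject than the whole-study difference of about 2.0 days (0.8 to 1.9 days larger if a recurrence takes 4 to 10 PE days). With half the follow-up relapses the excess is about 0.6 to 0.8 days. These figures rest on an assumed PE duration per recurrence, equal in both arms, and on Phase II recurrence patterns under a regimen without this trial's extension rule.

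A reader might infer that the plan is built to favour caplacizumab, or that the trial is bound to overstate the PE saved. The documents support neither. The rule treats both arms alike, the treatment-period tables are correctly labelled, and the direction in this trial depends on recurrence times not yet known. The endpoint is descriptive and outside the test hierarchy, so neither type I error nor power is affected. The change is worth making because it lets the trial answer its own objective.

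**What to change.** In SAP 3.3.2.2, SAP 6.2.2 and Tables 14.2.1.5.2 to 14.2.1.5.4:

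- Keep the two planned periods, and add the follow-up period and the overall study period for PE days and for absolute and normalized volume, by initial arm. The period definitions and arm grouping already exist for ICU and hospital days.
- Show the overall-study figure beside any treatment-period statement on PE use.
- Confirm that PE during follow-up is captured in the eCRF. Protocol 3.3.6 makes PE an eCRF item, but the follow-up schedule (protocol Table 3) has no PE row.
- State that PE still running at the final follow-up visit is truncated there.

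The cost is SAP wording and two more columns in three tables. The stated benefit on PE may turn out smaller.
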